Inclusion Criteria	Exclusion Criteria
Caregivers of a child between ages 9-18 who has either not received any HPV vaccine doses or has received only initial HPV dose	Caregivers whose child has completed additional HPV vaccine doses
Receives care at Adelante Healthcare Mesa	
Fluent in English and/or Spanish	
Willing to provide informed consent	

BIOSCIENCE INSTRUCTIONS AND TEMPLATE

NUMBER	DATE	PAGE
HRP-503b	3/31/2020	2 of 4

5 Number of Participants

90 participants will be enrolled in the study; 45 in the control group / 45 in the intervention group

6 Recruitment Methods

The study research assistants (RA) will work directly with the clinic during the study enrollment period to generate a list of all patients (and their caregivers) who may be eligible to participate in the study. Adelante office staff will search patients' online medical files to determine which individuals are age-eligible for the vaccine who have either 1) not initiated the vaccine series and/or 2) have only completed one of the HPV vaccine doses. They will generate a list of eligible patients with caregiver contact information to the RA.

The RA will use a vacant office space for all recruitment and enrollment activities. To initiate contact with potential participants, she will send a letter to caregivers of children eligible for HPV vaccine, inviting them to take part in a study about HPV vaccine intentions. The letter will contain study-specific phone number that will reach RA's office directly. RA will screen caregivers for eligibility and notify clinic staff of all patients/caregivers eligible for study. Caregivers will work with clinic staff to schedule an office visit. When the clinic staff schedules the patient's visit, they will ask caregivers to stay an addition 15-20 minutes after their scheduled appointment to complete the study informed consent and baseline surveys.

7 Study Timelines

We anticipate participants being a part of the study for up to 8 months. We expect that individuals will spend up to 2 hours (1 hour on 2 days) on completing study surveys, one on the first day of the study and another after six months. They will also spend time taking their child to receive the additional HPV vaccine doses.

8 Procedures Involved

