The project utilizes a software (REDCap) which randomizes individuals into intervention and control groups, using permuted block randomization. As participants enroll in the study, they will be given a study identification number (e.g. 1,2,3). Both the intervention and control groups will complete baseline surveys.

Control group participants will receive standard care and will be expected to return to Adelante Healthcare Mesa to receive the additional HPV vaccine booster doses. Intervention group participants will be referred to receive the additional HPV vaccine doses at their community pharmacy. At post-intervention, intervention participants will be asked if their children completed the HPV vaccine series.

Primary behavioral outcome: At the end of the 16-month intervention, PI will ask clinic staff to report HPV vaccination dose completion (for vaccine doses 1,2,3) for all study participants.

Follow-up Survey Data Collection: RA will call all participants and administer follow-up survey to measure potential changes in DOI theoretical constructs (see baseline survey).

Qualitative telephone in-depth interviews: To qualitatively explore intervention feasibility and acceptability, PI will conduct telephone interviews with patients, patients' caregivers, clinic primary care providers, and clinic pharmacists.

- In-depth interview with Caregivers and/or Young Adult Patients: PI will conduct telephone interviews with caregivers from the control group (standard care) and from the intervention group (pharmacist-administered HPV vaccination) related to their experiences taking part in the study.
- In-Depth interviews with Providers and Pharmacists: Researchers will conduct telephone interviews with all the clinic's participating primary health care providers and office manager (n= 4) and local pharmacists who work at pharmacies where patients were referred to receive the HPV vaccine (n=4) to explore their acceptability and perceived feasibility of the intervention. They will be asked how the intervention impacted the quality of patient care, ways in which the intervention impacted patient flow within the clinic, how satisfied they were with the intervention, and perceived fit of the intervention within their workplace.

Participant Incentives: Research participants will receive e-gift card incentives (of their choosing from Tango Card, Inc) for completing study surveys (\$20 dollars per survey completed) and for participating in telephone interviews (\$30).

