9 Withdrawal of Participants

There are no anticipated circumstances under which participants will be withdrawn from the research study without their consent.

If participants choose to no longer take part in this study, they are asked to contact the PI ([name], [contact]) to notify her that they will no longer be involved in the study. The PI will remove and destroy all participant data from the study.

BIOSCIENCE INSTRUCTIONS AND TEMPLATE

NUMBER	DATE	PAGE
HRP-503b	3/31/2020	3 of 4

10 Risks to Participants

There are no foreseeable risks to research participants. Risks of the HPV vaccine (a non-virus vaccine –which utilizes a protein which looks similar to HPV) include a fever, pain at injection site, and a headache. A much less common side effect of the vaccine is fainting within 15 minutes of injection. For this reason /risk, patients are told to remain at the clinic/pharmacy for an additional 15 minutes after they receive the vaccine to ensure that they are safe to leave.

11 Potential Benefits to Participants

HPV vaccine age-eligible children will complete the HPV vaccine series, thus preventing the risk of HPV-related cancers. Also, intervention participants will learn more about the role of the community pharmacist in administering vaccines and vaccine booster doses. This may help aid in the completion of vaccine series without having to schedule and revisit primary care providers' offices.

12 Setting

This study will be conducted at Adelante Healthcare Mesa, a local federally qualified health center. Intervention participants will be referred to receive additional HPV vaccine booster shots with their community pharmacists. Pharmacists are currently licensed to administer the HPV vaccine.

13 Multi-Site Research

NA

14 Resources Available

This clinically based study will take place at Adelante Healthcare Mesa, a Federally Qualified Health Center (FQHC) which predominantly serves ethnic/racial minority, low-income populations.

15 Prior Approvals

We have received prior approval and secured an MOU with Adelante Healthcare Mesa to conduct this study.

16 Data Management and Confidentiality
Data Analysis:
Aim 1 Data Analysis: Assessing Preliminary Efficacy.

The specific aim of the proposed project is to investigate the effect of CPVAC on HPV vaccination completion rate compared with primary care provider (Aim 1).

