Patient-related outcomes: Two proportion Z tests will be used to examine the proportion differences in HPV vaccination completion between CPVAC and primary care provider (PCP) groups. We will also compare which medical professionals completed the vaccine doses. We will create codes for various health care professionals (e.g. nurse, nurse practitioner, physician, pharmacist, etc.) to differentiate who administered the vaccine. The HPV completion status will be classified as dichotomous variable (0 = no; 1 = yes). Independent variables will be classified as either categorical or continuous scale: age, gender, race; location, HPV vaccine dose (1, 2, 3, etc); provider types (PCP vs pharmacist); facility type/place of service (health clinic vs. pharmacy). Multiple logistic regression with stepwise selection procedures will be used to identify whether these independent variables are associated with HPV completion status.

Psychosocial Constructs Data Analysis: Baseline characteristics of the study participants will be summarized using descriptive statistics. Multiple logistic regression will be used to investigate whether psychosocial factors (e.g. intention, norms, efficacy) relate to HPV vaccine completion (yes/no). General linear models or Mann-Whitney U tests will be used to test mean or median differences for self-efficacy and response-efficacy to complete the vaccine series between CPVAC and PCP groups.

Missing Data: We will conduct sensitivity analyses including imputation methods and completer-only analyses. All statistical procedures and analyses will be performed in SPSS software.

BIOSCIENCE INSTRUCTIONS AND TEMPLATE

NUMBER	DATE	PAGE
HRP-503b	3/31/2020	4 of 4

Aim 2 Data Analysis: Qualitatively exploring feasibility and acceptability of CPVAC

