PI will submit the interview audio-recordings to an ASU-approved transcription company. Using the interview guide to determine a priori themes, PI will create a coding book for the interview data. Reading through all interview transcripts, PI will add emerging themes to expand the coding guide. PI will train the RA in descriptive content analysis. They will review and code one transcript together, code an additional three transcripts separately, meet to discuss coding choices, and reach an agreement on data interpretations and analysis before they split the remaining interview transcripts for review. PI and RA will upload all transcripts and codes into ATLAS.ti software. PI will take the outcomes from the analyses from ATLAS.ti and begin to summarize findings for each in-depth interview question with the RA to ensure interpretation consensus and create a comprehensive summary of the findings related to intervention acceptability and feasibility.

Data Storage:

Patients' information will be de-identified and given a unique Participant Study Number for data analysis by an Adelante Healthcare Mesa healthcare practitioner. All signed informed consent documents will remain with the PI. She will secure them in a locked drawer of a locked office. These forms will be kept up to two years and will be destroyed at the end of those two years.

17 Safety Monitoring

[name] (PI) and the research assistants will meet on a monthly basis to evaluate the data collected for the study. They will review completeness of patient surveys and informed consent and updates related to HPV vaccine series completion.

18 Consent Process

The clinic will notify the RAs when potential participants have scheduled office visits. After the office visit, a nurse or office staff member will walk the patient to the RA's research office. The RA will briefly explain that this study is about HPV vaccine intentions and vaccine completion and invite caregivers to sign up for the study. If patients decide not to sign up that day, they will be given a study information sheet and a phone number to call should they decide to participate later. RA will also write down their contact information to follow up on study enrollment. For caregivers interested in signing up for the study, the RA will administer the informed consent and baseline surveys.

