The project biostatistician will have already generated a randomization table for the intervention and control groups, using permuted block randomization. As participants enroll in the study, they will be given a study identification number (e.g. 1,2,3). Based on their study number and the randomization table, they will be assigned to either intervention or control group.

For the in-depth interviews with caregivers (at post-intervention), the RA will contact participants via phone. The RA will administer informed consent via the phone and verbally consent participants prior to conducting the phone interviews.

19 Investigational New Drug or Devices

NA

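### Section 9 destroys all study data of families who actively withdraw, so randomised families leave the completion comparison and the planned imputation cannot cover them

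*Combined protocol and SAP*

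**What the plan says.** The trigger in Section 9 is an active step by the family: "If participants choose to no longer take part in this study, they are asked to contact the PI". The consequence follows: "The PI will remove and destroy all participant data from the study". No other section limits this.

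The sections that bear on it are:

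- **Section 5:** "90 participants will be enrolled in the study; 45 in the control group / 45 in the intervention group".
- **Section 8, primary behavioral outcome:** "PI will ask clinic staff to report HPV vaccination dose completion (for vaccine doses 1,2,3) for all study participants".
- **Section 8, intervention arm only:** "At post-intervention, intervention participants will be asked if their children completed the HPV vaccine series".
- **Section 16, Missing Data:** "We will conduct sensitivity analyses including imputation methods and completer-only analyses". The completion comparison in the same section is a two-proportion Z test, and no analysis population is named.
- **Section 17, on the monthly meetings:** "They will review completeness of patient surveys and informed consent and updates related to HPV vaccine series completion".
- **Section 18:** "The project biostatistician will have already generated a randomization table for the intervention and control groups, using permuted block randomization". Arm then follows from the study number given at enrolment.

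**The concern.** Assignment happens at enrolment, so withdrawal normally comes after randomisation. Deleting the record is then a post-randomisation exclusion, made by the family, who know which arm they are in. The arms differ visibly: one is sent to a community pharmacy, the other returns to its clinic. Withdrawal that depends on arm is therefore plausible, though nothing in the documents shows that it will occur.

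If withdrawal is related to both arm and completion, the difference is biased. It is biased upward if intervention non-completers leave and downward if control non-completers leave. The missing-data plan does not help, because imputation needs a retained record. Nor could anyone later check whether the withdrawn families differed at baseline, or had already finished the series as far as the study knew.

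**Working it through.** The plan has no figure to reproduce here: Section 5 gives 90 families without a significance level, power, effect size or dropout rate.

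**Inputs.** From the documents: 45 per arm and a two-proportion Z test. Assumed: two-sided 5% level, pooled variance, true completion p = 0.45 in both arms, and every withdrawal rate below. The 0.45 lies between the 37.5% (males) and 49.5% (females) cited in Section 2.

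**Shift from deletion.** If a share d of intervention non-completers is deleted, that arm's expected proportion becomes p / [p + (1 − p)(1 − d)]. Expected non-completers per arm are 0.55 × 45 = 24.75.

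- d = 4% (24.75 × 0.04 = 1.0 family): 0.45/0.978 − 0.45 = +1.0 points
- d = 8% (2.0 families): 0.45/0.956 − 0.45 = +2.1 points
- d = 20% (5.0 families): 0.45/0.890 − 0.45 = +5.6 points
- d = 40% (9.9 families): 0.45/0.780 − 0.45 = +12.7 points

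**Rejection under equal true rates.** These come from exact enumeration, each family withdrawing independently at the stated rate.

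| Records deleted | Shift (points) | Rejection |
|---|---|---|
| None | 0 | 4.6% |
| 4% of intervention non-completers | +1.0 | 5.1% |
| 8% of intervention non-completers | +2.1 | 5.5% |
| 20% of intervention non-completers | +5.6 | 8.2% |
| 40% of intervention non-completers (one-sided extreme) | +12.7 | 20.4% |
| 20% intervention and 10% control non-completers | +2.9 | 6.0% |
| 20% of non-completers in both arms | 0 | 5.1% |
| 20% of control non-completers | −5.6 | 8.2% |
| 1/45 or 2/45 of the intervention arm, unrelated to outcome | 0 | 5.0% or 5.1% |
| 20% of the intervention arm, unrelated to outcome | 0 | 5.1% |

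At one or two families, random loss gives nearly the same rejection rate as selective loss. The harm at that size is the 1–2 point shift, not the error rate.

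**Other completion rates.** With d = 20% in the intervention arm only, p = 0.30 gives 0.30/0.86 − 0.30 = +4.9 points (7.8%), and p = 0.60 gives 0.60/0.92 − 0.60 = +5.2 points (8.0%). These two values differ slightly, so equal deletion of non-completers in both arms gives exactly 0 only when the true rates are equal.

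**What survives deletion.** The withdrawn count per arm can probably be rebuilt from the randomisation table, gaps in the study numbers and the 45 + 45 target. Bounds then follow. With 20 known completers in an arm of 45, two withdrawn gives 20/45 = 44.4% to 22/45 = 48.9%. Five withdrawn gives 44.4% to 25/45 = 55.6%. The baseline survey cannot be rebuilt this way.

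**Check on possible repairs.** Suppose 20% of the intervention arm withdraws unrelated to outcome. Deletion then gives 0 points.

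- *Coding withdrawn families as non-completers:* 0.45 × 0.80 − 0.45 = −9.0 points, 13.6% rejection.
- *Adding back only known completers, half of the withdrawn completers having finished before leaving (assumed):* (0.36 + 0.045)/(0.36 + 0.045 + 0.44) − 0.45 = 0.405/0.845 − 0.45 = +2.9 points.
- *Using clinic-reported final status when the record misses a share m of these families' completions:* −0.45 × 0.20 × m, that is −4.5 points at m = 50% and −9.0 at m = 100% (m assumed). Only with full capture is the shift 0.

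**The case against.** **The harm shown is small.** The rule reaches only families who contact the investigator. Those who merely miss the follow-up survey are untouched. One or two selective withdrawals shift the difference by 1–2 points, against a standard error of √(2 × 0.45 × 0.55/45) = 10.5 points. The larger shifts need 20–40% of one arm's non-completers to withdraw actively, which nothing in the documents supports. This is a pilot of preliminary efficacy. All of this stands and limits the weight of the point. It does not remove it, because the deletion is irreversible and the safeguard is cheap.

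**A reader might infer that the outcome of withdrawn families is freely available, since the clinic reports it.** The documents do not support that for the intervention arm. Those doses are given at outside pharmacies, and no section says how they reach the clinic record. Section 8 separately asks intervention families about completion. The definition calls for a clinic report; whether that report is complete is not established.

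**A reader might also infer that dose histories are lost for good.** That is too strong. Section 9 concerns data in the study, and nothing says the clinic's file is destroyed. What goes is the study baseline data, any dose status the study holds, and probably the link and permission to use the clinic record. That the study stores doses child by child is itself an inference from the monthly review in Section 17.

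**Erasure is a legitimate privacy commitment to families of minors.** It is, and the consent pages are not visible here. That is a reason to put the least intrusive change first.

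**Conclusion.** The concern holds in limited form. As written, Section 9 takes actively withdrawing randomised families out of the completion comparison and out of reach of the planned imputation.

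The size cannot be stated, because no withdrawal rate is given. Under the assumed 45% completion and 45 per arm, a few selective withdrawals cost 1–2 points. About five in the intervention arm alone cost 5.6 points, with 8.2% rejection. Loss unrelated to outcome costs nothing in bias. A reader might take the 12.7-point figure as a forecast; it is a one-sided extreme with no support in the documents.

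The plan should be changed. Confidence is medium, because both the number of withdrawals and their relation to completion are unknown.

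**What to change.** 1. **Minimum.** Keep the allocation list and an anonymous count of withdrawals by arm, report the count, and give best/worst-case bounds by arm. This needs little or no narrowing of the deletion promise.
2. **Preferably also.** Amend Section 9, and the consent text if it repeats the promise, with IRB agreement. Withdrawal should stop further contact, while coded data collected to that date (arm, baseline survey, any dose status held) stay in the randomised arm, unless the family asks for erasure.
3. **Where the family and the IRB allow.** Keep the clinic-reported final dose status as well. Use it in the main analysis only if doses given at community pharmacies are shown to reach the clinic record, for withdrawn and remaining families alike. Otherwise confine it to sensitivity analyses, because missed pharmacy doses would bias the intervention arm downward.
4. **For families without usable final status.** Report, as sensitivity analyses, imputation where baseline data are kept, non-completer coding, and the bounds. Do not make non-completer coding, or adding back only known completers, the main analysis.

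The cost is a protocol amendment, and possibly a consent amendment. The downside is that the deletion promise concerning minors' health information is narrowed. Without dependable final status, no single rule for withdrawn families is free of bias, which is why several are reported.

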BIOSCIENCE INSTRUCTIONS AND TEMPLATE

NUMBER	DATE	PAGE
HRP-503b	3/31/2020	1 of 4

1 Protocol Title

Community Pharmacists Vaccinating Against Cancer (CPVAC): A Pilot Randomized Controlled Trial Aimed at Increasing HPV Vaccine Completion Rates Among Racially/Ethnically Diverse Youth

2 Background and Objectives

The majority of HPV-related cancers and genital warts can be prevented through the timely uptake and completion of the HPV vaccine series.^{23,25,26} Human papillomavirus (HPV) is the most common sexually transmitted infection, and persistent infection with oncogenic HPV strains cause cancer.²⁷ The HPV strains most commonly associated with cancer are HPV 16 and 18. However, strains 31, 33, 35, 39, 45, 51, 52, 56, 58, and 59 are also carcinogenic.²⁸ Commercially available 9-valent HPV vaccines offer the potential of immunity against seven oncogenic strains (Types 16, 18, 31, 33, 45, 52, 58) and the two low-risk strains (Types 6 and 11) that cause over 90% of genital warts.²⁹ Vaccine completion is critical because it boosts the body's ability to fight off the virus.³

In 2016 only 37.5% of HPV vaccine age-eligible males and 49.5% of females completed the HPV vaccine series⁷ with racial/ethnic minorities exhibiting lower rates of completion.⁸ Specifically, Black and Latino children and young adults have a higher rate of initiation of the vaccine;⁹ however, they have a significantly lower likelihood of completing the vaccine series.⁹ Further, Latino patients who prefer speaking Spanish as opposed to English have lower HPV vaccine completion rates.¹⁰ It is critical to enhance HPV vaccine series completion among racial/ethnic minority HPV vaccine age-eligible individuals to reduce cancer disparities. Barriers to complete the HPV vaccine have included the following: lack of time to receive the follow-up vaccines,¹¹ transportation needed to return for follow-up clinical visits,¹¹ additional office co-pays,³¹ lack of awareness to receive additional HPV vaccine doses,³² and Lack of strong provider recommendation for vaccine initiation/completion³⁴ particularly for male patients.

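### The completion comparison uses no baseline data: a prespecified adjusted risk difference would cost little and could give a precision gain that ranges from none to moderate

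*Combined protocol and SAP*

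**What the plan says.** All references are to the combined protocol and SAP.

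- **Arm comparison.** In section 16, under Aim 1, the paragraph on outcomes in patients states: "Two proportion Z tests will be used to examine the proportion differences in HPV vaccination completion between CPVAC and primary care provider (PCP) groups". No covariate, alpha or sidedness is given.
- **Stepwise model.** The same paragraph plans a stepwise logistic regression for completion. Its candidates are age, gender, race, location, dose number, provider type and facility type. Randomised arm is not listed.
- **Psychosocial model.** Section 16 also plans a logistic regression on whether "psychosocial factors (e.g. intention, norms, efficacy) relate to HPV vaccine completion (yes/no". It names no arm term and does not say when the factors are measured.
- **Baseline data.** Section 8: "Both the intervention and control groups will complete baseline surveys". The content is described only as Diffusion of Innovation constructs, by reference to a survey that is not in the reviewed text.
- **Prognostic information.** Section 2 states that "only 37.5% of HPV vaccine age-eligible males and 49.5% of females completed the HPV vaccine series".
- **Size and allocation.** Section 5: "90 participants will be enrolled in the study; 45 in the control group / 45 in the intervention group". Sections 8 and 18 describe permuted blocks and name no stratification factor.

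**The concern.** The plan treats psychosocial factors as possible predictors of completion and lists age and gender among its variables, but uses none of them when it compares the arms. With 45 per arm and no named stratification, a chance difference between arms in a real predictor carries straight into the completion difference. If the baseline data predict completion, the reported interval is also wider than it needs to be.

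The other two models do not fill the gap. One has no arm term named. The other selects variables by stepwise search and includes dose number, provider type and facility type, which arise after randomisation and in part reflect the intervention itself. At stake is the precision of the Aim 1 estimate in a trial where precision is already scarce.

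**Working it through.** **1. Inputs.** From the documents: 45 per arm; an unadjusted Z test; completion of 37.5% (males) and 49.5% (females) in the 2016 background data. Assumed, because not stated: two-sided alpha of 0.05; control completion between 37.5% and 49.5%, midpoint 43.5%; an equal sex split; the prognostic strength of any baseline score.

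**2. Benchmark.** The documents give no power, effect size or rates with the figure of 90, so it cannot be reproduced. For reference, power = Φ[(d√n − 1.96√(2p̄(1−p̄))) / √(p₁(1−p₁)+p₂(1−p₂))], where d is the difference and n the number per arm. At n = 45, 80% power needs a difference of 29.2, 28.8 or 28.1 points for control rates of 37.5%, 43.5% or 49.5%. At 43.5% against 68.5%, power is 67.1% and the 95% CI half-width is 1.96 × √((0.2458 + 0.2158)/45) = 19.8 points.

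**3. Chance imbalance.**
- A factor present in 50% of children: SD of the between-arm difference = √(2 × 0.25/45) = 0.105, or 10.5 points.
- A standardised score: SD = √(2/45) = 0.21. The chance of exceeding 0.25 SD in either direction is 24%.
- Effect of a 0.25 SD imbalance on the unadjusted difference: √R² × √(0.435 × 0.565) × 0.25. This gives 2.8, 3.9, 5.5 and 6.8 points at R² of 0.05, 0.10, 0.20 and 0.30.

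**4. What the documented sex gap supports.** R² = 0.25 × 0.12² / (0.435 × 0.565) = 0.0036/0.2458 = about 1.5%. A 1-SD imbalance in sex moves the completion difference by 0.105 × 0.12 = 1.3 points. The standard error with 43.5% in both arms is √(2 × 0.2458/45) = 10.5 points. Adjusting for gender alone would therefore change little.

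**5. What a stronger predictor would give.** Two simulations (2,500 and 3,000 trials per setting, 45 per arm) compared the raw difference with a logistic-standardised risk difference adjusted for a baseline score, sex and age. Predictor strengths are assumed.

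| OR per SD of score | Variance ratio, adjusted/unadjusted | 90 adjusted is worth about | Half-width, from 19.8 |
|---|---|---|---|
| 1.0 | 1.02 | 90/1.018 = 88 | 20.0 |
| 1.5 | 0.99 | 90/0.991 = 91 | 19.7 |
| 2.0 | 0.93 | 90/0.925 = 97 | 19.0 |
| 2.7 | 0.82 to 0.85 | 90/0.82 = 110 to 90/0.85 = 106 | 17.9 to 18.3 |

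Half-widths are 19.8 × √ratio. The mean risk difference was the same with and without adjustment (0.188 and 0.189 in one run, 0.185 and 0.185 in the other), so the target quantity does not change. A 0.25 SD imbalance moved the unadjusted difference by 2.0, 3.6 and 5.0 points at odds ratios of 1.5, 2.0 and 2.7. It moved the adjusted difference by under 0.2 points.

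**6. Cost of useless covariates.** A further simulation (3,000 trials per setting, 43.5% against 68.5%) used one prognostic covariate plus three useless ones.
- R² about 0.055: power went from 66% to 65%, no gain.
- R² about 0.17: from 65% to 71%.
- R² about 0.26: from 68% to 77%.
- All four useless: from 66% to 63%, with a variance ratio of (0.1054/0.1036)² = 1.035.

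**7. Validity.** With no true difference, the Z test rejected in 4.1% to 5.1% of simulated trials.

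**The case against.** The case for leaving the plan alone is substantial. An unadjusted comparison of two proportions is valid under randomisation, transparent and widely accepted. This is a pilot assessing preliminary efficacy, with no power target that the Z test fails to meet. The one prognostic figure in the documents implies almost no gain, and it describes age-eligible youth in general, not children recruited at this clinic. A material gain needs an odds ratio of 2 or more per SD, which nothing in the documents establishes. All of this stands, and it limits the size of the point. It does not remove it, because the possible loss is smaller than the possible gain and the choice must be fixed before outcomes are seen.

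One could also answer that age, gender and race are already modelled, and that the provider-type variable might stand for arm, since the control arm is called the PCP group. The text leaves that open. Even on that reading, the term would be subject to stepwise selection and would sit beside facility type and dose number, so the model would not give a prespecified adjusted arm effect.

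Three stronger readings are tempting, and the documents do not support them:
- **That every family supplies baseline intention and efficacy scores.** This is a reasonable inference. However, the survey is not in the text, and those constructs are named only in an analysis with no time point.
- **That the Z test is biased.** Randomisation protects it, as the simulated error rates show.
- **That adjustment removes both imbalance and imprecision.** It acts only on measured covariates in the model, and it improves precision only if they predict completion.

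**Conclusion.** The point holds as a low-cost improvement in efficiency. It does not correct an error. The only between-arm analysis of completion is unadjusted, and no other planned model supplies a baseline-adjusted arm effect.

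The gain runs from none to moderate: a variance change from about +2% (uninformative score) to −15% to −18% (odds ratio of 2.7 per SD). In the middle of that range the half-width falls by less than one point. These figures rest on assumed completion rates and assumed predictor strengths. The documented sex gap, at an R² of about 1.5%, supports only the bottom of the range. The upper part depends on a baseline score that the sponsor must first confirm is collected.

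**What to change.** In section 16, replace the sole reliance on the Z test with the following:

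- Prespecify one logistic model for completion with randomised arm forced in and a short fixed list of baseline covariates: age, gender and, if the baseline survey collects it, the baseline intention score. Use no stepwise selection and no post-randomisation variables.
- Report the risk difference standardised over all randomised children, with a robust or bootstrap 95% CI.
- Replace a missing baseline score by the overall mean and add a missing flag, so that no child is dropped.
- Keep the Z test as the unadjusted supportive result.

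The sponsor should confirm the baseline survey items and fix the list before seeing outcome data.

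The cost is a few sentences, with no new data if the score is already collected. If the covariates prove uninformative, the variance loss is about 2% with score, sex and age, rising to about 3.5% with four useless covariates, so the list should stay short. Some extra programming is needed: section 16 commits all analyses to SPSS, and whether standardisation with a bootstrap or robust interval is practical there should be checked first.
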